12.3.2 Evaluation of Non-Target Lesions

Complete Response (CR): Disappearance of all non-target lesions.

Non-CR/Non-PD: Persistence of one or more non-target lesion(s).

Progressive Disease (PD): Appearance of one or more new lesions and/or unequivocal progression of existing non-target lesions on stable or increasing doses of corticosteroids compared with baseline scan or best response after initiation of therapy* not caused by comorbid events (e.g. radiation therapy, demyelination, ischemic injury, infection, seizures, postoperative changes, or other treatment effects). Unequivocal progression should not normally trump target lesion status. It must be representative of overall disease status change, not a single lesion increase.

Although a clear progression of “non-target” lesions only is exceptional, the opinion of the treating physician should prevail in such circumstances, and the progression status should be confirmed at a later time by the review panel (or Principal Investigator).

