5. Patients who have undergone a resection for recurrence will be eligible. In those who have undergone a gross total resection, the MLA will be directed at treating a peritumoral margin of 0.5-1cm surrounding the resection cavity to disrupt the BBB and potentially increase access of MK-3475 to the peritumoral infiltrating glioma cells.
6. At least 18 years of age.
7. Karnofsky $\geq 60\%$ (see Appendix A)
8. Normal bone marrow and organ function as defined below:
 - a. ANC $\geq 1,500/\text{mcL}$
 - b. Platelets $\geq 100,000/\text{mcL}$
 - c. Hemoglobin $\geq 9 \text{ g/dL}$ or $\geq 5.6 \text{ mmol/L}$
 - d. Serum creatinine $\leq 1.5 \times \text{IULN}$ OR creatinine clearance by Cockcroft-Gault $\geq 60 \text{ mL/min}$ for patients with serum creatinine $> 1.5 \times \text{IULN}$
 - e. Serum total bilirubin $\leq 1.5 \times \text{IULN}$ OR direct bilirubin $\leq \text{IULN}$ for patients with total bilirubin $> 1.5 \times \text{IULN}$
 - f. AST (SGOT) and ALT (SGPT) $\leq 2.5 \times \text{IULN}$
 - g. INR or PT $\leq 1.5 \times \text{IULN}$ unless patient is receiving anticoagulant therapy as long as PT or PTT is within therapeutic range of intended use of anticoagulants
 - h. aPTT $\leq 1.5 \times \text{IULN}$ unless patient is receiving anticoagulant therapy as long as PT or PTT is within therapeutic range of intended use of anticoagulants
9. Sexually active women of childbearing potential and men must agree to use contraceptive methods as described in Section 5.8 prior to study entry, for the duration of study participation, and for 120 days after last dose of MK-3475. Should a woman become pregnant or suspect she is pregnant while participating in this study, she must inform her treating physician immediately.
10. Patients with the ability to understand and willingness to sign an IRB approved written informed consent document will be enrolled into the trial. However, should a patient lose their ability to consent while participating in this study and s/he is still receiving clinical benefit from participation, s/he may continue on study with the consent of a Legally Authorized Representative.

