Partial response	
Requires all of the following:
 
 $\geq 50\%$ decrease compared with baseline in the sum of products of perpendicular diameters of all measurable enhancing lesions sustained for at least 4 weeks. No progression of nonmeasurable disease. Stable or improved nonenhancing (T2/FLAIR) lesions on same or lower dose of corticosteroids compared with baseline scan; the corticosteroid dose at the time of the scan evaluation should be no greater than the dose at time of baseline scan. Stable or improved clinically. Note: Patients with nonmeasurable disease only cannot have a partial response; the best response possible is stable disease.
Stable disease	
Requires all of the following:
 
 Does not qualify for complete response, partial response, or progression. Stable nonenhancing (T2/FLAIR) lesions on same or lower dose of corticosteroids compared with baseline scan. In the event that the corticosteroid dose was increased for new symptoms and signs without confirmation of disease progression on neuroimaging, and subsequent follow-up imaging shows that this increase in corticosteroids was required because of disease progression, the last scan considered to show stable disease will be the scan obtained when the corticosteroid dose was equivalent to the baseline dose.
Progression	
Defined by any of the following:
 
 $\geq 25\%$ increase in sum of the products of perpendicular diameters of enhancing lesions compared with the smallest tumor measurement obtained either at baseline (if no decrease) or best response, on stable or increasing doses of corticosteroids*. The absolute increase in any dimension must be at least 5mm when calculating the products. Significant increase in T2/FLAIR nonenhancing lesion on stable or increasing doses of corticosteroids compared with baseline scan or best response after initiation of therapy* not caused by comorbid events (e.g. radiation therapy, demyelination, ischemic injury, infection, seizures, postoperative changes, or other treatment effects).

Response	Criteria

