	
 • Any new measureable lesion. • Clear clinical deterioration not attributable to other causes apart from the tumor (e.g. seizures, medication adverse effects, complications of therapy, cerebrovascular events, infection, and so on) or changes in corticosteroid dose. • Failure to return for evaluation as a result of death or deteriorating condition; or clear progression of nonmeasurable disease.

- NOTE. All measurable and nonmeasurable lesions must be assessed using the same techniques as at baseline.
- Abbreviations: MRI, magnetic resonance imaging; FLAIR, fluid-attenuated inversion recovery.
- Stable doses of corticosteroids include patients not on corticosteroids.

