12.2 Disease Parameters

Measurable disease: Bi-dimensionally measurable lesions with clearly defined margins by MRI scan of ≥ 10 mm. All tumor measurements must be recorded in millimeters (or decimal fractions of centimeters).

Non-measurable or evaluable disease: Uni-dimensionally measurable lesions or lesions with margins not clearly defined such as areas of T2/FLAIR signal abnormality or poorly defined enhancing abnormality.

Note: For cystic lesions, the only measurable part is any enhancement area around the cyst that is clearly defined and bi-dimensionally measurable. The cyst itself should not be considered measurable or non-measurable disease.

Target lesions: All measurable lesions that are seen at baseline MRI. Target lesions should be selected on the basis of their size (lesions with the longest diameter), but in addition should be those that lend themselves to reproducible repeated measurements. It may be the case that, on occasion, the largest lesion does not lend itself to reproducible measurement in which circumstance the next largest lesion, which can be measured reproducibly should be selected. When there are too many measurable lesions, choose the largest 3 lesions as target lesions to follow. The other measurable lesions should be considered evaluable for the purpose of objective status determination.

Non-target lesions: All non-measurable lesions should be identified as non-target lesions and should also be recorded at baseline. Measurements of these lesions are not required, but the presence, absence, or in rare cases unequivocal progression of each should be noted throughout follow-up.

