12.3.3 Evaluation of Best Overall Response

The best overall response is the best response recorded from the start of the treatment until disease progression/recurrence (taking as reference for progressive disease the smallest measurements recorded since the treatment started). The patient's best response assignment will depend on the achievement of both measurement and confirmation criteria.

Summary of the RANO Response Criteria (Adapted from JCO 2010)

Criterion	CR	PR	SD	PD
T1 gadolinium enhancing disease	None	$\geq 50\% \downarrow$	$< 50\% \downarrow$ but $< 25\% \uparrow$	$\geq 25\% \uparrow^*$
T2/FLAIR	Stable or \downarrow	Stable or \downarrow	Stable or \downarrow	\uparrow^*
New lesion	None	None	None	Present*
Corticosteroids	None	Stable or \downarrow	Stable or \downarrow	NA†
Clinical status	Stable or \uparrow	Stable or \uparrow	Stable or \uparrow	\downarrow^*
Requirement for response	All	All	All	Any*

Abbreviations: RANO, Response Assessment in Neuro-Oncology; CR, complete response; PR, partial response; SD, stable disease; PD, progressive disease; FLAIR, fluid-attenuated inversion recovery; NA, not applicable.

* Progression occurs when this criterion is present.

† Increase in corticosteroids alone will not be taken into account in determining progression in the absence of persistent clinical deterioration.

NOTE: Patients may continue on treatment and remain under close observation and evaluation at 4-8 week intervals if there is uncertainty regarding whether pseudoprogression may be present as determined by the investigators. If subsequent radiographic or clinical assessments suggest that the patient is in fact experiencing progression, then the date of progression should be the time point at which this issue was first raised. Similarly, stable disease may be assigned in cases of presumed “pseudoprogression” associated with decreased steroid use.

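### Section 12.3.2 restricts non-target progression that Sections 12.1 and 12.3.3 accept on its own, and no text says which rule sets the PFS event

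*Combined protocol and SAP*

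**What the plan says.** - **Section 12.1, response table.** Progression needs any one of the listed criteria. One is "Significant increase in T2/FLAIR nonenhancing lesion on stable or increasing doses of corticosteroids", provided it is not caused by comorbid events or treatment effects. Another is "Failure to return for evaluation as a result of death or deteriorating condition; or clear progression of nonmeasurable disease". Neither depends on the status of the target lesions.
- **Section 12.3.3, summary table.** An increase in T2/FLAIR is starred in the PD column, the requirement for PD is any starred item, and the footnote reads "Progression occurs when this criterion is present".
- **Section 12.2.** Non-measurable disease includes "lesions with margins not clearly defined such as areas of T2/FLAIR signal abnormality or poorly defined enhancing abnormality", and "All non-measurable lesions should be identified as non-target lesions".
- **Section 12.3.2.** PD includes "unequivocal progression of existing non-target lesions on stable or increasing doses of corticosteroids", with the same exclusion of comorbid and treatment effects. It then adds "Unequivocal progression should not normally trump target lesion status. It must be representative of overall disease status change, not a single lesion increase". It calls clear non-target-only progression exceptional, gives the treating physician's opinion priority in such cases, and asks for later confirmation by a review panel or the Principal Investigator.
- **Section 12.3.6.** PFS runs from start of treatment to progression or death. It does not say which of these sections defines progression.
- **Sections 2.1 and 15.4.** PFS is the phase II primary endpoint. It is tested with a two-sided one-sample log-rank test in 32 patients against a historical median of 2.9 months.

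**The concern.** The rules meet on one kind of scan: target lesions stable, one T2/FLAIR or ill-defined enhancing lesion clearly larger, steroids stable, no other cause. Section 12.1 calls this progression. Section 12.3.2 gives two reasons not to: target status normally prevails, and a single lesion's growth is not enough.

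Such scans are plausible here. Section 1.2 reports that peritumoral enhancement and FLAIR signal rose significantly two weeks after MLA and persisted for several weeks, so readers will have to judge non-target change.

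Compared with applying 12.1, using 12.3.2 to withhold PD can only move a PFS event later or remove it. The trial is open-label, has one arm, and uses a fixed external comparator, so no concurrent group would share the delay.

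**Working it through.** **1. The same scan under each section**

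| Finding: stable targets, one clearly growing T2/FLAIR or ill-defined lesion | Result |
|---|---|
| 12.1 (any criterion; steroid and cause conditions met) | PD |
| 12.3.3 (T2/FLAIR increase starred; any suffices) | PD if the lesion is T2/FLAIR |
| 12.3.2, PD definition | PD if unequivocal |
| 12.3.2, restriction that follows | Normally not PD |
| 12.3.2, physician clause | Case by case, confirmed later |

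New lesions are outside the conflict: all three sections count them.

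**2. The plan's own power figure**

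Inputs from Section 15.4: n = 32, medians 5.1 and 2.9 months, accrual 20 months, further follow-up 6 months, two-sided alpha 0.05. Exponential PFS and uniform accrual are assumed.

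- Hazards: ln 2 / 2.9 = 0.2390 and ln 2 / 5.1 = 0.1359 per month.
- Under the alternative, observed events per patient p1 = 0.8480. Events expected at the control hazard p0 = 0.8480 × 5.1/2.9 = 1.4913.
- Variance of observed minus expected per patient under the alternative (Wu formula): 2.0382.
- Power = Φ{[√32 × (1.4913 − 0.8480) − 1.96 × √1.4913] / √2.0382} = Φ{(3.639 − 2.394)/1.428} = Φ(0.872) = 80.85%. The plan states 80.9%, so the figure is reproduced.
- Expected events: about 27 of 32 at a median of 5.1 months, and 30 of 32 at 2.9 months.

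**3. What late calls would do if there were no benefit**

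The simulation used n = 32, exponential PFS with true median 2.9 months, and censoring uniform from 6 to 26 months. The statistic is Z = (O − E)/√E with E at hazard 0.2390, and a false benefit is Z < −1.96. Each scenario had at least 60,000 trials. A random share of events is called late by up to one scan interval (Section 12.1: 9 weeks, or 63/30.44 = 2.07 months). The share is **assumed**; the documents give none. In the last column, a second event at the control hazard (also assumed) can end the delay early.

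| Share called late | False benefit, full 9-week delay | Observed median, full delay (months) | False benefit, delay can end early |
|---|---|---|---|
| 0% | 1.6% | 2.9 | 1.6% |
| 5% | 2.3% | 3.0 | 2.2% |
| 10% | 3.1% | 3.2 | 2.6–2.8% |
| 20% | 5.3% | 3.4 | 4.2–4.3% |
| 30% | 8.4% | 3.6 | 6.3–6.4% |

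Repeat runs differ by about 0.1 to 0.3 percentage points. The nominal one-sided level is 2.5%. With no delay the test sits below it on the benefit side, so at a 5% share it is still within the nominal level.

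**The case against.** The best defence is that 12.3.2 is a caution about when progression is unequivocal. It lists non-target progression as PD with conditions much like those of 12.1. The physician clause can be read as permitting a PD call on non-target lesions alone, and nothing in it re-dates the event. Caution is also reasonable given the FLAIR changes reported after MLA. All of this stands, so a reader should not infer that 12.3.2 excludes non-target PD. The conflict remains, because the clause settles cases by individual judgement and does not say which section governs.

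Other text limits the damage. New lesions, clinical deterioration and death are events in any case. The 12.3.3 note back-dates progression to the time when doubt was first raised, though only where pseudoprogression was in question.

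Four stronger readings are tempting but unsupported:

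- **Gross total resection.** Section 3.1 says "In those who have undergone a gross total resection, the MLA will be directed at treating a peritumoral margin", and such a patient may have no target lesion. One might infer that growth at the margin can never count. But there is then no target status to override, and a single lesion may be the whole disease.
- **Bevacizumab.** Section 5.7 allows it as a steroid-sparing agent, and 12.1 links T2/FLAIR increase to antiangiogenic therapy. That sentence is in the table for first progression after chemoradiotherapy and is permissive.
- **Complete response.** 12.3.2 requires non-target lesions to disappear, while 12.1 needs only stable or improved T2/FLAIR. This cannot change PFS.
- **A 10% to 30% share as an estimate.** 12.3.2 itself calls clear non-target-only progression exceptional. The simulation also picks events at random, deaths included.

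**Conclusion.** The inconsistency is real and concerns the primary endpoint: one scan can be PD under 12.1 and 12.3.3 and not PD under 12.3.2, and no text says which sets the PFS event. This conclusion does not depend on the simulation.

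The bias is conditional. It arises only where 12.3.2 is used to withhold a call that 12.1 would make, and it then favours the treatment arm. A reader might infer that PFS is biased upward in every case; the documents do not support that, because the physician clause may produce the same call as 12.1.

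The size cannot be derived from the documents. Over assumed shares of 5% to 30%, with delays of up to 9 weeks and a true median of 2.9 months, the false-benefit rate is about 2.2% to 8.4%, against 1.6% with no delay. At the low end the effect is negligible. At the high end it is more than three times the nominal 2.5% (8.4/2.5 = 3.4). The sample size of 32 and the stated power are unaffected.

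**What to change.** Reconcile Sections 12.1, 12.3.2 and 12.3.3, and state in 12.3.6 or Section 15 one rule for the PFS event and its date.

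- **Rule.** The natural candidate for the analysis is the any-criterion rule of 12.1, with its existing steroid and comorbid or treatment-effect conditions. Section 12.1 adopts RANO for response and progression, and the 12.1 response table and 12.3.3 summary are labelled as adapted from that publication.
- **Date.** Align the event date with the pseudoprogression back-dating note in 12.3.3.
- **Application.** Apply the rule to scans already collected as well as to future ones, and record which calls change.
- **Scope.** This concerns the analysis event only. When progression ends treatment is a separate clinical matter for the sponsor to reconcile.

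The cost is wording and a re-read of the affected scans. No new imaging is needed. Estimated PFS may come out slightly less favourable.

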12.3.3 Evaluation of Best Overall Response

The best overall response is the best response recorded from the start of the treatment until disease progression/recurrence (taking as reference for progressive disease the smallest measurements recorded since the treatment started). The patient's best response assignment will depend on the achievement of both measurement and confirmation criteria.

Summary of the RANO Response Criteria (Adapted from JCO 2010)

Criterion	CR	PR	SD	PD
T1 gadolinium enhancing disease	None	$\geq 50\% \downarrow$	$< 50\% \downarrow$ but $< 25\% \uparrow$	$\geq 25\% \uparrow^*$
T2/FLAIR	Stable or \downarrow	Stable or \downarrow	Stable or \downarrow	\uparrow^*
New lesion	None	None	None	Present*
Corticosteroids	None	Stable or \downarrow	Stable or \downarrow	NA†
Clinical status	Stable or \uparrow	Stable or \uparrow	Stable or \uparrow	\downarrow^*
Requirement for response	All	All	All	Any*

Abbreviations: RANO, Response Assessment in Neuro-Oncology; CR, complete response; PR, partial response; SD, stable disease; PD, progressive disease; FLAIR, fluid-attenuated inversion recovery; NA, not applicable.

* Progression occurs when this criterion is present.

† Increase in corticosteroids alone will not be taken into account in determining progression in the absence of persistent clinical deterioration.

NOTE: Patients may continue on treatment and remain under close observation and evaluation at 4-8 week intervals if there is uncertainty regarding whether pseudoprogression may be present as determined by the investigators. If subsequent radiographic or clinical assessments suggest that the patient is in fact experiencing progression, then the date of progression should be the time point at which this issue was first raised. Similarly, stable disease may be assigned in cases of presumed “pseudoprogression” associated with decreased steroid use.

12.3.4 Duration of Response

Duration of overall response: The duration of overall response is measured from the time measurement criteria are met for CR or PR (whichever is first recorded) until the first date that recurrent or progressive disease is objectively documented (taking as reference for progressive disease the smallest measurements recorded since the treatment started).

The duration of overall CR is measured from the time measurement criteria are first met for CR until the first date that progressive disease is objectively documented.

Duration of stable disease: Stable disease is measured from the start of the treatment until the criteria for progression are met, taking as reference the smallest measurements recorded since the treatment started, including the baseline measurements.

12.3.5 Neurological Exam and Performance Status

Patients will be graded using the Karnofsky Performance Status scale and their neurological function evaluated as improved, stable or deteriorated in addition to objective measurement of tumor size. These parameters will be used to determine the overall response assessment.

12.3.6 Progression-Free Survival

PFS is defined as the duration of time from start of treatment to time of progression or death, whichever occurs first.

13.0 DATA AND SAFETY MONITORING

In compliance with the Washington University Institutional Data and Safety Monitoring Plan, an independent Data and Safety Monitoring Board (DSMB) will be specifically convened for this trial to review toxicity data. A DSMB will consist of no fewer than 3 members including 2 clinical investigators and a biostatistician. Like investigators, DSMB members are subject to the Washington University School of Medicine policies regarding standards of conduct. Individuals invited to serve on the DSMB will disclose any potential conflicts of interest to the trial principal investigator and/or appropriate university officials, in accordance with institution policies.

Potential conflicts that develop during a trial or a member's tenure on a DSMB must also be disclosed.

Until such a time as the first secondary site enrolls its first patient, a semi-annual DSM report to be prepared by the study team will be submitted to the Quality Assurance and Safety Monitoring Committee (QASMC) semi-annually beginning six months after study activation at Washington University (if at least one patient has been enrolled) or one year after study activation (if no patients have been enrolled at the six-month mark).

The DSM report will be prepared by the study team with assistance from the study statistician, will be reviewed by the DSMB, and will be submitted to the Quality Assurance and Safety Monitoring Committee (QASMC). The DSMB must meet at least every six months beginning six months after study activation at Washington University or beginning six months after enrollment of the first patient at a secondary site, no more than one month prior to the due date of the DSM report to QASMC.

During the phase I dose escalation, the Principal Investigator will review all patient data at least monthly (or before each dose escalation if occurring sooner than monthly), and provide a semi-annual report to the QASMC. During the phase II, the Principal Investigator/DSMB will review all patient data at least every six months, and provide a semi-annual report to the QASMC. This report will include:

- HRPO protocol number, protocol title, Principal Investigator name, data coordinator name, regulatory coordinator name, and statistician
- Date of initial HRPO approval, date of most recent consent HRPO approval/revision, date of HRPO expiration, date of most recent QA audit, study status, and phase of study
- History of study including summary of substantive amendments; summary of accrual suspensions including start/stop dates and reason; and summary of protocol exceptions, error, or breach of confidentiality including start/stop dates and reason
- Study-wide target accrual and study-wide actual accrual including numbers from participating sites
- Protocol activation date at each participating site
- Average rate of accrual observed in year 1, year 2, and subsequent years at each participating site
- Expected accrual end date, accrual by site, and accrual by cohort
- Objectives of protocol with supporting data and list the number of participants who have met each objective
- Measures of efficacy
- Early stopping rules with supporting data and list the number of participants who have met the early stopping rules
- Summary of toxicities at all participating sites separated by cohorts with the number of dose-limiting toxicities indicated
- Abstract submissions/publications
- Summary of any recent literature that may affect the safety or ethics of the study

Further DSMC responsibilities are described in the DSMC charter.

Until such a time as the first secondary site activates this protocol, a semi-annual Data and Safety Monitoring report to be prepared by the study team will be submitted to the QASM Committee beginning 6 months after study activation at Washington University.

The study principal investigator and coordinator will monitor for serious toxicities on an ongoing basis. Once the principal investigator or coordinator becomes aware of an adverse event, the AE will be reported to the HRPO and QASMC according to institutional guidelines (please refer to Section 7.0).

Refer to the Washington University Quality Assurance and Data Safety Monitoring Committee Policies and Procedures for full details on the responsibilities of the DSMC at <https://siteman.wustl.edu/research/clinical-research-resources/protocol-office-prmcqasmc/>.

